5.4.6. Procedure for termination of or withdrawal from the study

If possible, perform a complete follow-up visit for subject who withdraws from the study, including a physical examination, vital signs, an ECG test and a laboratory test (Refer to Study Flow Chart Table 1, 2 and 3). To evaluate AEs or laboratory abnormalities and ensure that they are reversible or stable, follow-up visits will be conducted at an appropriate time for all subjects who withdraw after the last dose of the investigational product. Results will be recorded in the original medical record and eCRF. The reasons for withdrawal will also be recorded in the original medical record and eCRF.

6 TREATMENT REGIMEN

6.1. Randomization and blinding method

6.1.1. Randomization method

Subjects meeting all eligibility criteria of study stage 1 will be randomized into the study and stratified according to whether the subject had previous failure of a tumor necrosis factor (TNF)- α antagonist therapy.

Sub-study 1 of the study stage 2 will include subjects who have achieved clinical response by adapted Mayo score in the 12-week induction therapy in study stage 1 as shown by efficacy evaluation and who meet eligibility criteria for entering study stage 2: they will receive blinded maintenance treatment with the regimen used during study stage 1. Sub-study 2 of the study stage 2 will include subjects who have not achieved clinical response by adapted Mayo score in the induction therapy in study stage 1 and who meet eligibility criteria for stage 2: they will receive open-label treatment with CBP-307 0.2 mg/day.

6.1.2. Allocation of subjects

In study stage 1,_subjects will be randomly assigned to one of the following 2 groups in a 1:1 ratio:

- CBP-307 0.2 mg, once daily
- Placebo, once daily

In study stage 2, subjects included in sub-study 1 will continue treatment with the regimen used during stage 1. Subjects included in sub-study 2 will receive oral treatment with CBP-307 0.2 mg once daily after dose titration.

6.1.3. Blinding and blinding process

The study stage 1 is a randomized, double-blind, placebo-controlled clinical study, and substudy 1 of the study stage 2 will aim at investigating the long-term safety and efficacy in subjects who have achieved clinical response in study stage 1 by continuing with the double-blind treatment. Sponsor, the clinical team entrusted by the CRO, the investigator, the clinical center's personnel involved in the study and the subjects do not know to which group subjects are randomly assigned throughout the study.

In case of an emergency, the investigator has the responsibility for determining if unblinding of a subject's treatment assignment is warranted. Subject safety must always be the first consideration in making such a determination. Generally, sponsor must be informed of unblinding in advance, unless in urgent cases where unblinding is necessary for the medical treatment of the subject, sponsor must be notified within 48 hours after unblinding. The date and reason for unblinding must be entered into the clinical trial management database.

The investigator should not perform unblinding recklessly. If unblinding occurs, the subject's participation in the trial will be discontinued, but they should remain in the study for 4-week safety follow-up.

Sub-study 2 of the study stage 2 will be open-label treatment with a dose of 0.2 mg/day of CBP-307, so blinding process is not applicable.

6.2. Treatment regimen

Oral administration within half an hour after meal at 7:00~10:00 am every day. If possible, subjects should try to keep taking the drug at a similar time point every day.

Dose regimen of the dose titration period in the study stage 1

Subjects in CBP-307 group will undergo dose titration for 1 week while those in placebo group will undergo simulated titration. Both CBP-307 and placebo will be administered through the oral route. For subjects in the group of CBP-307 0.2 mg once daily, a dose of 0.05 mg CBP-307 will be given from day 1 to day 4; then, a dose of 0.1 mg CBP-307 will be given for later 3 days; from day 8, a target dose (0.2 mg) will be administered.

Detailed steps for dose titration are in Table 5.

Table 5. Titration dosing regimen

Target dose	Day 1 to day 4	Day 5 to day 7	From day 8
CBP-307 0.2 mg	0.05 mg	0.1 mg	0.2 mg
Placebo	Placebo capsules	Placebo capsules	Placebo capsules

Note: During the titration period, CBP-307 0.05 mg will be orally administered at doses of 0.05 mg (1 capsule) and 0.1 mg will be orally administered at 0.05mg (2 capsules); in the placebo group, placebo capsules at the corresponding quantity (completely identical with CBP-307 in appearance and weight) will also be orally taken. From day 8, in the 0.2 mg group, 2 capsules of 0.1 mg will be orally administered; and in the placebo group, 2 capsules of placebo (completely identical with CBP-307 in appearance and weight) will also be orally taken. The drugs taken daily will be sub-packaged in bottles in a GMP-compliant workshop, the investigational product will be independently packaged in boxes based on visit intervals.

Dose regimen of the dose titration in study stage 2

Subjects included in sub-study 1 of study stage 2 are no longer required to undergo dose titration. Subjects included in sub-study 2 (open-label treatment) of stage 2 will undergo 1-week dose titration. Dose titration involves administration of CBP-307 0.05 mg initiated on day 1 for 4 consecutive days, followed by administration of CBP-307 0.1 mg for 3 days, and administration of CBP-307 at a target dose of 0.2 mg initiated on day 8.

Dose titration in the sub-study 2 of stage 2 are in Table 6.

Protocol No.: CBP-307CN002 Confidential

Table 6. Administration regimen dose titration in study stage 2

Target dose	Day 1 to day 4	Day 5 to day 7	From day 8		
CBP-307 0.2 mg/day	0.05 mg/day	0.1 mg/day	0.2 mg/day		

Note: During the titration period, CBP-307 0.05 mg will be achieved with 1 capsule of 0.05 mg strength and 0.1 mg will be achieved with 2 capsules of 0.05mg strength; From day 8, 2 capsules of 0.1 mg will be administered. The drugs taken daily will be sub-packaged in bottles in a GMP-compliant workshop, the investigational product will be independently packaged in boxes based on visit intervals.

6.2.1. Cardiac monitoring during titration

In study stage 1, detailed schedule for cardiac monitoring during titration is provided in Table 7.

In the stage 2 sub-study 2, detailed schedule for cardiac monitoring during titration is provided in Table 8.

Table 7. Stage 1 Cardiac monitoring

	Cardiac monitoring											
	Titration day 1				Titration day 2				Titration day 5 and day 8			
Monitoring method	Before administration	Every hour within the 6 h after administration	The 4th hour and 6th hour	Continuous monitoring for 24 hours		Every hour within the 6 h after administration	The 4th hour and 6th hour	Continuous monitoring for 24 hours	administration	within the	6th hour	Continuous monitoring for 24 hours
Vital signs	X	X	X^3		X	X	X^3		X	X	X^3	
12-lead ECG	X		X^3		X		X^3		X		X^3	
Holter monitoring	X ¹			X^2					X^2			X^2

Notes:

- 1. 24-hour Holter monitoring before day 1 will be initiated 1 day before drug administration (baseline day 0).
- 2. 24-hour Holter monitoring will be initiated from 30min ±10min before drug administration until 24 ho urs after drug administration.
- 3. Subjects still need further monitoring in the following cases:
 - at 6 hours after drug administration, the subject's heart rate is still < 45 times/min;
 - at 6 hours after drug administration, the subject's heart rate is still at the lowest level after drug administration;
 - at 6 hours after drug administration, 12-lead ECG shows newly-occurring second degree or higher degree atrioventricular block;
 - at 6 hours after drug administration, the QTcF interval is prolonged (> 450 ms in males; > 470 ms in females);
 - at 6 hours after drug administration, if the subject has symptomatic bradycardia, they will be monitored until it has resolved.

Table 8. Sub-study 2 of Study Stage 2 Cardiac Monitoring

	Cardiac monitoring											
	Titration day 1				Titration day 2				Titration day 5 and day 8			
Monitoring method	Before administration	Every hour within the 6 h after administration	The 4th hour and 6th hour	Continuous monitoring for 24 hours	administration	Every hour within the 6 h after administration	The 4th hour and 6th hour		administration	within the	6th hour	Continuous monitoring for 24 hours
Vital signs	X	X	X^3		X	X	X^3		X	X	X^3	
12-lead ECG	X		X^3		X		X^3		X		X ³	
Holter monitoring	X ¹			X^2					X^2			X^2

Notes:

- 1. 24-hour Holter monitoring before day 1 will be initiated 1 day before drug administration.
- 2. 24-hour Holter monitoring will be initiated from 30min ±10min before drug administration until 24 hours after drug administration.
- 3. Subjects still need further monitoring in the following cases:
 - at 6 hours after drug administration, the subject's heart rate is still < 45 times/min;
 - at 6 hours after drug administration, the subject's heart rate is still at the lowest level after drug administration;
 - at 6 hours after drug administration, 12-lead ECG shows newly-occurring second degree or higher degree atrioventricular block;
 - at 6 hours after drug administration, the QTcF interval is prolonged (> 450 ms in males; > 470 ms in females).
 - at 6 hours after drug administration, if the subject has symptomatic bradycardia, they will be monitored until it has resolved.

6.2.2. Missing dose

Subjects should be informed that they can take a missed dose within 4 hours after the normal time for oral administration; otherwise they will need to take the drug of original dose at the normal time on the following day. If subjects experience vomiting after taking the capsules, they do not need to re-take the drug on the same day but need to take the drug at the original dose at the normal time on the following day. If subjects cannot take the drug due to other medical conditions, which leads to dose discontinuation, they are required to contact the investigator in time.

On occasions of missed doses:

- Within the first 2 weeks of treatment, if dose is missed for more than 1 day (2 to 7 days interruption), the drug dosing needs to be restarted at the site and the first-dose monitoring procedures need to be repeated for subjects.
- After 2 weeks of treatment, if the dosing is missed no more than 2 days, subjects can take the original dose at the normal time on the following day; if the dosing is interrupted for 3 to 7 consecutive days, the drug will need to be restarted at the site with proper oversight. ECG will be performed before dose administration and at 4 and 6 hours after dose; vital signs will be monitored hourly. However, there will be no 24-hour Holter monitoring.

Subjects, except those who experience dose discontinuation due to a significant decrease in the peripheral lymphocyte count, will be required to withdraw from the study if the dose is discontinued for more than 7 days (see Section 8.6 for details).

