- have achieved clinical response will enter study stage 2 sub-study 1 (maintenance treatment period) and continue their treatment in study stage 1. The interval between the first administration of sub-study 2 and the last administration of study stage 1 will be less than 1 week.
- 2. Subjects are recommended to be followed up in the morning. At the indicated visits, subjects will be given medication at the site. If time permits, subjects in the study should be evaluated at roughly the same time. For subjects who cannot continue to participate in the study for any reason, the investigator should make every effort to complete the evaluation during the end of the study/early termination of the follow-up visit.
- 3. The signing of informed consent can also be done at visit 11 of study stage 1 (week 12).
- 4. The Quantiferon or Quantiferon Plus of the screening of stage 1 can be used as the basis. However, if the subjects had a history of exposure to TB patients during study stage 1, or suspected TB infection, the Quantiferon or Quantiferon Plus assay should be performed again. If possible, the blood samples of the Quantiferon or Quantiferon Plus assay could be collected at visit 11 (week 12). If the Quantiferon or Quantiferon Plus results are negative, the subject could be included in the study. If the Quantiferon or Quantiferon Plus results are indeterminate, they can be tested again. If the Quantiferon or Quantiferon Plus results are still indeterminate, the patient should not be included. If the Quantiferon or Quantiferon Plus repeat test results are negative, the subject could be enrolled.
- 5. Only patients who do not have abnormal chest radiographs at visit 11 of study stage 1 are allowed to be included; during the study period, the investigator may review the chest X-ray or chest CT according to the clinical situation.
- 6. The 12-lead ECG will be examined at 4 hours after administration and 6 hours after administration at visit 12, and will be examined at 4 hours after administration at the remaining visits (except the follow-up visit after treatment ends). The time window for 12-lead ECG is + / 0.5 hours.
- 7. Vital signs include heart rate, blood pressure, body temperature and respiratory rate. Vital signs will be checked before administration.

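### At visit 12, Table 3 gives sub-study 1 entrants lighter restart monitoring than Protocol 6.2.2 sets for a dosing gap of the same length

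*Protocol*

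**What the plan says.** Section 6.2.2 of the Protocol (Missing dose) grades the response to a gap after the first 2 weeks of treatment.

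- Short gap: "if the dosing is missed no more than 2 days, subjects can take the original dose at the normal time on the following day".
- Longer gap: "if the dosing is interrupted for 3 to 7 consecutive days, the drug will need to be restarted at the site with proper oversight". The monitoring is then specified: "ECG will be performed before dose administration and at 4 and 6 hours after dose; vital signs will be monitored hourly". No Holter is needed.
- Beyond that, subjects "will be required to withdraw from the study if the dose is discontinued for more than 7 days", apart from those stopped for a low lymphocyte count.

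The visit charts set the days. Table 2 makes visit 11 (Day 84 ±5) the last-dose visit of stage 1, with the dose taken on site. Table 3 places visit 12, the stage 2 screening visit for sub-study 1, at Day 90 ±5. It marks both dispensing and the recording of the dosing time there. Section 6.2 states that sub-study 1 entrants are not re-titrated.

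For monitoring at visit 12, Table 3 note 6 reads: "The 12-lead ECG will be examined at 4 hours after administration and 6 hours after administration at visit 12". The vital-signs row is blank at visit 12. Note 7, which governs the marked visits, says only: "Vital signs will be checked before administration". Table 3 does not refer to 6.2.2.

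Table 3 note 1 limits the gap: "The interval between the first administration of sub-study 2 and the last administration of study stage 1 will be less than 1 week". It names sub-study 2 in the sub-study 1 chart. The same sentence stands in Table 4 note 1, so this looks like a copying slip.

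**The concern.** CBP-307 lowers heart rate. Section 3.4.4 places the fall at 2 to 4 hours after a dose, and section 8.6 reports it on the first two days of dosing at clinically relevant doses. Section 7.5 says that the effect fades over time after receptor desensitization. The restart rule in 6.2.2 is the protocol's own standard for resuming the drug after several days off it.

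A site that follows Table 3 on the nominal days would resume the full assigned dose after 5 undosed days with no pre-dose ECG and no vital signs. A rhythm finding at 4 or 6 hours would have no same-day comparator. Nothing would be recorded in the first 3 hours, when part of the expected fall occurs. The issue is subject safety and consistent site practice. No efficacy endpoint, error rate or sample size is affected.

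**Working it through.** The plan states no figure to reproduce. The check is a day count and a comparison of two schedules.

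**1. Nominal gap.** Undosed days = day of first stage 2 dose − day of last stage 1 dose − 1. With Day 84 (Table 2, visit 11) and Day 90 (Table 3, visit 12): 90 − 84 − 1 = 5, namely Days 85 to 89. This lies inside the 3-to-7-day range of 6.2.2.

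**2. Range under the cap.** An interval of less than 1 week is at most 6 days from dose to dose, hence at most 5 undosed days. The visit 12 window opens on Day 85. For a last dose on Day 84:

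| First sub-study 1 dose | Undosed days | 6.2.2 restart range |
|---|---|---|
| Day 85, 86, 87 | 0, 1, 2 | not reached |
| Day 88, 89, 90 | 3, 4, 5 | reached |

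**3. Monitoring of the same dose, side by side.**

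| Item | 6.2.2, 3 to 7 days | Table 3, visit 12 |
|---|---|---|
| ECG before dosing | yes | no |
| ECG at 4 h and 6 h | yes | yes |
| Hourly vital signs | yes | none marked |
| Holter | no | no |

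The chart falls short by the pre-dose ECG and the whole vital-signs series.

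**4. Is a gap of this length pharmacologically a restart?** Section 3.4.1 gives a half-life of about 25 hours. Six days is 144 hours, so the fraction left is 0.5^(144/25), about 2%. As a check, section 3.4.3 gives an AUC accumulation ratio of 2.8 at 0.15 mg daily. Under simple linear kinetics, the fraction left per day is 1 − 1/2.8 = 0.643, and 0.643^6 is about 7%. Both figures come from healthy volunteers. On either one, little drug remains on Day 90. The documents give no heart-rate data on resuming the drug after 12 weeks of treatment.

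**5. Timing.** Hourly vital signs would give readings at 1, 2 and 3 hours, before the first ECG listed in Table 3.

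**The case against.** The strongest reply is that 6.2.2 does not govern this dose. Its heading and its examples (late doses, vomiting, medical conditions) concern doses that a subject should have taken but did not. A gap produced by the visit schedule, with its own cap, is arguably something else. Note 6 also adds a 6-hour ECG at visit 12 where the other on-treatment visits have only the 4-hour one, which suggests that the sponsor considered this dose and chose its monitoring. If 6.2.2 does apply, it is a conditional rule that overlays every chart, and Tables 2 and 4 do not restate it either.

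Much of this stands. A reader might infer that Table 3 flatly contradicts a requirement, and the documents do not support that: 6.2.2 is silent on the stage transition, and Table 3 does not forbid extra monitoring. But the silence cuts both ways. The operative word in 6.2.2 is interruption, and no exemption is given. Nor is a dose-free gap planned elsewhere. The synopsis describes stage 2 dosing as continuous, section 5.3 counts 48 weeks of administration over both stages, and SAP section 12 plans 42 dosing days from Day 84 to Day 126. A note that gives a shorter ECG list without a pointer to 6.2.2 leaves sites to guess.

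A reader might also take section 7.5 step a as already requiring vital signs at visit 12. It can equally be read as an instruction on posture, and section 7.3.2 refers the timing back to the flow charts.

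The risk is limited. The 4-hour and 6-hour ECGs remain, and visit 11 supplies an earlier 4-hour post-dose ECG. Section 3.4.4 reports no cardiac adverse events at single doses of 0.1 to 0.5 mg, and 6.2.2 itself treats late interruptions more lightly than early ones.

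**Conclusion.** The point holds as a gap between two schedules. On the protocol's nominal days, sub-study 1 entrants have 5 undosed days, and the chart prescribes less than the protocol's own standard for a gap of that length. The conclusion rests on the nominal days and on reading the cap in Table 3 note 1 as meant for sub-study 1.

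Three stronger readings go too far.

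- That every entrant is affected. Table 3 note 3 allows stage 2 consent at visit 11, so entry with 0 to 2 undosed days is possible and 6.2.2 then asks nothing extra. Central reading of the week 12 colonoscopy may make next-day entry difficult, but that is an inference. The share affected is unknown.
- That the visit 12 window lets gaps run past the 7-day withdrawal limit. The under-1-week cap excludes this once its wording is corrected.
- That the change merely restates existing duties. Whether 6.2.2 covers the transition is exactly what the text leaves open.

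The safety gain is modest. The change is worth making because it is cheap and removes an ambiguity at a full-dose restart.

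**What to change.** In Table 3:

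1. Mark vital signs, before dosing, at visit 12.
2. Add to notes 6 and 7 that, if 3 or more days were undosed since the last stage 1 dose, a pre-dose ECG and hourly vital signs to 6 hours are added to the 4-hour and 6-hour ECGs.
3. In note 1, change sub-study 2 to sub-study 1.

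In section 6.2.2, state that the gap between the last stage 1 dose and the first stage 2 dose counts as an interruption. The trigger should be the number of undosed days and never the treatment arm: placebo entrants carry no restart risk, but sub-study 1 is blinded.

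The cost is one table cell, three notes and one sentence. Every entrant gains one pre-dose set of vital signs. Affected entrants also gain one ECG and about six hourly sets, at a visit already held on site through the 6-hour ECG. No Holter is needed.

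Stating instead that the transition is exempt from 6.2.2 would also end the ambiguity. It would leave the lighter monitoring in place, so it would need a stated reason.

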6.3. Labeling and packaging of the investigational product

The investigational product will be provided by sponsor: Suzhou Connect Biopharmaceuticals Ltd.

The label of the investigational product will contain the following information:

- Statement that it is used for clinical study only
- Warning "Please keep out of reach of children"
- Sponsor's name and production address
- Drug name (a statement: "CBP-307 or Placebo")

- Drug number
- Protocol No.
- Dosing instructions
- Storage condition
- Shelf life
- Batch No.

6.4. Distribution of investigational product

In study stage 1, the investigator or his/her designee will register subjects in an electronic data capture system (Medidata RAVE) at screening, complete randomization using the RAVE Randomization and Trial Supply Management (RTSM) system, and obtain random numbers in RAVE and dispense drugs accordingly. Before drug dispensing, a drug identifying number will be provided by the RAVE RTSM system and displayed in real time in RAVE, so that the study site's investigator or his/her designee is accessible to the identifying number. If the drug provided by sponsor is lost or damaged, the study site's investigator or his/her designee will complete drug replacement procedures on RAVE's interface. At visits for drug dispensing, the investigator or his/her designee will access the RAVE as the above to keep a record of drug dispensing and return.

Subjects who complete the study stage 1 and enter sub-study 1 of study stage 2 will receive double-blind maintenance treatment for 36 weeks (weeks 13-48) with the same regimen used in the stage 1. The approach to drug dispensing is the same as that in the stage 1. Subjects who complete study stage 1 and enter sub-study 2 of study stage 2 will enter open-label treatment with CBP-307 0.2 mg/day. Subjects, regardless of whether they receive CBP-307 0.2 mg or placebo in stage 1, will receive CBP-307 at an oral dose of 0.2 mg once daily in sub-study 2 of the study stage 2. Drugs for open-label treatment will be directly distributed by the investigator, and their ID numbers are entered into the RAVE.

Note: For the subjects already enrolled as per the previous approved protocols (version 5.0 or earlier), they will follow the previous planned treatment until they finish the study.

6.5. Accountability of investigational product and treatment compliance

6.5.1. Accountability of investigational product

CBP-307 capsules and placebo should be stored at controlled 2-8°C. The investigational product must be stored in a cabinet according to the storage conditions on the label. The cabinet

will be locked and managed by a specially designated person.

The study site's investigator or his/her authorized representative (such as a pharmacist) will ensure that the investigational product is stored in a safe area in accordance with the recommended storage conditions and regulations.

The investigator must keep a detailed accountability record containing the information on the receipt, use, loss, or other disposal of the investigational product. To maintain a complete record, all drugs will be described in detail in the drug quantity and inventory record, and at each visit, the drugs that are not used yet and returned by the subject will be counted.

After the end of the trial, sponsor will instruct how to dispose of the unused investigational product. If sponsor authorizes the study site to dispose of the drug, the investigator must ensure that the materials are disposed of in accordance with relevant regulatory requirements and the hospital's procedures, and then, disposal will be recorded well. At the end of the study, the subject cannot take the investigational product anymore.

